1.0 Objectives

1.1 The overall objectives of the research grant are listed below; patients and providers will be involved in the data collection for Aims 1 & 2 whereas Aim 3 & 4 will not have any patient involvement and will assess costs of implementation from a system standpoint and plans for dissemination:

Aim 1: Test the effectiveness of an EHR-based Medication Complete Communication (EMC²) strategy, with and without SMS text reminders to improve patient understanding and use of opioid medications.

Aim 2: Evaluate the fidelity of the EMC² Strategies and explore patient, provider, and health system barriers to the implementation and effectiveness of either intervention.

Aim 3: Assess the costs required to deliver the interventions, exclusive of system design.

Aim 4: Develop a dissemination plan for the EMC², with any necessary modifications, to other emergency departments and relevant medical practices.

1.2 Related to Aim 1 above, we hypothesize that leveraging an electronic health record (EHR) based Medication Complete Communication (EMC²) strategy will reduce medication errors with newly prescribed opioid medications demonstrated by patient use compared to usual care. Compared to those receiving usual care, patients receiving the EMC² strategies will:

H1 Report higher rates of provider (physician and pharmacist) counseling

H2 Have a greater understanding of risks associated with newly prescribed opioid medications

H3 demonstrate more appropriate safe use of prescribed high-risk opioid medications

2.0 Background

2.1 Research has repeatedly demonstrated that individuals lack essential information on how to safely take medication they are prescribed.¹⁻⁶ Knowledge deficits are greatest for information pertaining to risks and warnings.⁷ This general lack of awareness is a leading root cause of the many cases of misuse that have translated to serious adverse events.

2.2 Neither physicians nor pharmacists routinely counsel patients to ensure understanding, leaving patients to rely on product labeling, such as the package insert, container label, or medication

EHR-Based Medication Complete Communication (EMC²) Strategy to Promote Safe Opioid Use: A Physician Randomized Trial

leaflets.⁸⁻¹² These existing tools that have been designed to inform individuals on the safe, appropriate use of a prescribed(R_x) medication - including risks and warnings – are limited in their effectiveness. Even when evidence-based practices are employed to develop these written communications, those with limited literacy and numeracy skills - and older adults - may remain at greater risk for poor understanding and medication errors.¹³⁻¹⁵

Poor understanding of medication risks is particularly concerning for opioid pain relievers. In the past decade, there has been a marked increase of opioid prescriptions and a corresponding increase in the number of deaths from both opioid abuse and unintentional misuse.¹⁶⁻²⁰ In 2008, opioid pain relievers were involved in 74% of all deaths from prescription drug overdose.¹⁶ Widely variable and often inadequate patient counseling about this class of medications may contribute to this, especially in the Emergency Department (ED) where pain is the most common complaint and opioid pain relievers the most commonly prescribed medication.²¹⁻²⁶ 39% of all opioids are prescribed in the ED, yet both spoken and written counseling is minimal.²⁷⁻²⁹

At the national level, the Food and Drug Administration (FDA) and Drug Enforcement Agency (DEA) endorse health system interventions targeting long-acting and extended release opioids and have focused many efforts on the physician prescriber.^{17,30} To date, the ED response has also been to focus on the prescriber by trying to reduce inappropriate opioid prescribing.³¹⁻³⁶ Yet interventions are also needed to improve the prevalence and quality of patient education and counseling at the time of appropriate prescribing.

- 2.3 With the increasing adoption of EHRs and mobile technologies, we now have the ability to impart risk information to individuals at multiple time points and via multiple modalities. We will implement an EHR-based, Medication Complete Communication (EMC2) strategy, wherein 1) emergency physicians adequately counsel patients at the time of prescribing, 2) tangible tools reinforce counseling, and 3) a mechanism for follow-up engages additional providers to reinforce education and confirm understanding.

3.0 Inclusion and Exclusion Criteria

3.1 Screening for eligibility for study

Emergency Department Providers. The research study will be described to providers by the emergency department leadership and study leadership, both via email and at in-person business meetings. All ED providers

EHR-Based Medication Complete Communication (EMC²) Strategy to Promote Safe Opioid Use: A Physician Randomized Trial

(attending MD, resident MD, NP, PA) with the exception of study investigators will be eligible. Providers will be asked to complete a written consent form if they choose to be involved in the study.

Patients. During the patient recruitment period, the RA will make frequent rounds through the ED and ask physicians to identify potentially eligible patients who will be discharged home on opioid pain relievers. The RA also will carry a pager so that physicians can notify the RA if they have an eligible patient. This method of patient identification has a well-established track record within our ED for maximizing enrollment while minimizing RA downtime. If the patient is interested in participating or learning more about the study, the RA will obtain verbal permission to ask the patient a brief series of questions to determine eligibility (see criteria below). If the patient is eligible for the study, the RA will proceed with obtaining written informed consent.

Follow-up Providers. Certain providers will interact with consented patients after the intervention takes place (e.g. Primary care physicians (PCP) and outpatient pharmacists). These providers will have no required role in carrying out the intervention (which is carried out by the EHR enhancements). These providers will be identified by chart review (PCP) and pill bottle review (pharmacists) at the time of patient follow-up. <30% of ED patients have on-staff PCP and there is no way to predict where the patients will fill their prescriptions (e.g., on-site Walgreens or another pharmacy). After identifying these providers at the time of follow-up, we will contact them via email or mail to participate in a survey. Both types of surveys will be offered to accommodate providers' busy schedules and because the pharmacists are located at diverse locations across the city of Chicago. The survey will assess the implementation of the EHR interventions and the providers' reactions to receiving additional information about their patients who were prescribed opioids in the ED.

3.2 **ED Provider Inclusion Criteria.** 1) Resident, Attending Physician or Mid-level provider (NP, PA) working in the Northwestern Emergency Department during study dates.

ED Provider Exclusion Criteria. 1) Study investigator.

Patient Inclusion Criteria. To be eligible to enroll and remain in the study, patient subjects must meet all of the following criteria: 1) Patient age 18 years and older, 2) English language speaking 3) prescribed pill form of hydrocodone-acetaminophen opioid pain reliever 4) the patient is the person primarily responsible for administering medication

Patient Exclusion criteria. Subjects will be excluded from the study if any of the following conditions are met: 1) Aged <18, 2) non-English

EHR-Based Medication Complete Communication (EMC²) Strategy to Promote Safe Opioid Use: A Physician Randomized Trial

speaking, 3) clinically unstable, psychologically impaired or intoxicated as judged by research staff member or emergency physician, 4) chronic opioid use, defined as daily or near daily use of opioid pain relievers for the past 90 days 5) admitted to hospital 6) unable to complete follow up phone interviews 7) pregnant

Follow-up Provider Inclusion Criteria: 1) Primary care physician within Northwestern system who has seen patient enrolled in study as part of routine ED follow-up or 2) Pharmacist who filled opioid prescriptions for study participant.

Follow-up Provider Exclusion Criteria: none

3.3 Special Populations

No special or vulnerable populations will be included.

4.0 Study-Wide Number of Subjects

- 4.1 Number of Emergency Department Physicians and Mid-Level providers to be enrolled. N=150
- Number of Patients to be Enrolled. N=1500
- Number of follow up providers to be enrolled (PCP/Pharmacists) N=50

5.0 Study-Wide Recruitment Methods

N/A

6.0 Multi-Site Research

N/A

7.0 Study Timelines

An individual ED physician or mid-level provider will be involved in this study for a maximum of two years of patient enrollment.

An individual patient subject will be involved in the study for a total of 1 month. They will complete a baseline enrollment interview, a phone interview at 2-4 days, a phone interview at 7-14 days, and a final phone interview at 1 month.

An individual PCP or pharmacist will be involved in the study for the amount of time it takes to complete the survey questionnaire (estimated at approx. 5-10 minutes).

We anticipate that patient enrollment will actively take place for 1.5 years to reach the target N above; however if accrual occurs at a slower rate we have allowed 2 years. The estimated date to complete primary analyses is May 2017.

8.0 Study Endpoints

8.1 Covariates. Baseline assessment will include a sociodemographic and health questionnaire and questions about previous use of opioids. A literacy assessment using the Newest Vital Sign (NVS) will be performed.

Primary Endpoint. Demonstrated understanding of how to properly dose the opioid medication as measured by participants' ability to correctly dose their prescription regimen using a demonstrated dosing exercise previously used in studies by both Drs. [name] and [name]. Primary endpoint will be assessed at the 7-14 day phone interview.

Secondary Endpoint. Actual use of the opioid medication as measured through the review of the medication diary, participant report of refills and new opioid prescriptions received patient opinion of the intervention as measured by both closed and open-ended questions at the time of follow-up phone interview; patient risky-behaviors while on opioids, as measured by patient self-report. Other aspects of safe use related to *risk awareness* will be assessed using a questionnaire, as will beliefs about medication use. The questionnaire will assess topics including safe storage of opioids, sharing of opioids, disposal on completion of the prescription, and questions related to possible dangerous behaviors. Secondary endpoints will be assessed with phone interviews .

Tertiary Endpoints. The identification of medication names, dosage, risks, warnings, and benefits will be assessed through a structured questionnaire that has been developed and used extensively by [name] and colleagues in multiple studies and current NIH-funded grants. The self-report of provider counseling will also be measured. Tertiary endpoint assessments will be assessed via phone interviews.

Exploratory Endpoint. A subset of analyses will examine return visits to the ED (obtained via EDW query) and admission to the hospital for a complaint related to opioid pain reliever (ranging from mild, e.g., constipation to severe, e.g., respiratory depression). Additional analyses will be conducted to evaluate for possible misuse or inappropriate prescribing. Outcome indicators include: 1) opioid overlap (defined as opioid prescriptions that overlap by 7 or more days, including refills), 2) opioid and benzodiazepine overlap, 3) long acting/extended release opioid prescription written for acutely painful conditions 4) high daily opioid dosage (defined as a prescribed daily dose of 100 morphine milligram equivalents (MME) or greater) and 5) opioid dose escalation (measured as having a 50% or greater increase in mean MME per month twice during the year).^{91,92} These data will be obtained by a data pull via the Illinois

EHR-Based Medication Complete Communication (EMC²) Strategy to Promote Safe Opioid Use: A Physician Randomized Trial

Prescription Monitoring Program (ILPMP) at 1-year post initial ED prescription. Drs. [name] and [name] will conduct this data-pull. Patients PHI will not be sent to the ILPMP or any other state or pharmacy governing body to obtain these data.

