The initial study visit (baseline) will be conducted at the time of patient enrollment. Following this baseline interview, RAs will conduct three telephone interviews (at 2-4 days post-baseline, 7-14 days post-baseline and at one month post-baseline). The first two assessments (at enrollment and 2-4day follow-up call) have been included to closely track patient recall of counseling and knowledge, while the latter two assessments (7-14 day follow-up call and 1 month follow-up call) are included to assess decay of knowledge, safe use, storage of medications and demonstrated dosing. The final call (one month post-baseline) will assess disposal of

EHR-Based Medication Complete Communication (EMC²) Strategy to Promote Safe Opioid Use: A Physician Randomized Trial

medications and determine if patients have received additional opioid pain relievers from other providers.

Baseline Interview. At the time of enrollment, the RA will ask the participant to indicate the best days and times to call within a 2-4 day range. A \$5 Gift card given to the participant for completion of enrollment tasks.

First Study (2-4 Day) Phone Call. The study phone call will be conducted at a time of convenience for the patient, however still within a 2-4 day range post-baseline. Additionally during this phone call, the RA will either confirm or schedule the 7-14 day follow-up call. A \$10 Gift card will be mailed to the participant for completion of first phone call.

Second Study (7-14 Day) Phone Call. The second phone call will be conducted at a time of convenience for the patient, however still within 7-14 day range post-baseline. Patients will be compensated for their time to complete the call with a \$20 gift card which will be mailed to the participant upon completing the call. Patients will also be asked to mail back their de-identified medication diary using the prepaid envelope provided at baseline.

Third/Final Study (1 Month) Phone Call. The final study phone call will be conducted at a time of convenience for the patient, however still within 1-month post-baseline. (See Attached Interview script)

Intervention Patients with physicians randomized to the EMC² arm will receive the 5-part EMC2 intervention.

[figure not shown]

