Patients with ED physicians randomized to the EMC² +SMS Text reminder arm will receive the above-described 5 components of the EMC² intervention, and also will receive daily text reminders for one week (7 messages) following the new prescription for an opioid pain reliever (only consented patients). The premise for the 1-week timeframe is to help patients remember precautions regarding safe use during the time they are taking the medication (average ED Rx for opioids is from pilot data is 18 tabs). Furthermore, SMS text reminders that would continue indefinitely are at risk for either being ignored, irritating patients, and/or adding an unnecessary expense to patients (i.e., patient does not have an unlimited texting plan, further challenging sustainability). Messages sent early in the week will focus on topics such as safe storage and use; those sent near the end of the week will focus on topics such as disposal and pill sharing. We will schedule EMC² text messages to arrive mid-day (12:00pm to 5:00pm), based on patient preference. (See appendix for sample text messages)

9.3 Procedures to monitor safety and minimize risk.

As a part of all of the time points of follow-up, the RAs will have a checklist of potentially dangerous behaviors related to opioids and if these items are noted in the course of data collection the RAs have a set protocol to follow. (see safety protocol attached)

9.4 The drug hydrocodone-acetaminophen is the topic of the research; however it is not being used in the research—the intervention is focused on education about this medication and the study will not change the drug, dose, frequency, quantity or refills that the ED physician selects in the course of their normal clinical care.

Sources of Materials:

Electronic Health Record (EHR): Patient information and outcomes will be extracted from the EHR (demographics, ED return visits and re-admissions). Re-admissions and re-visits to the hospital and ED data will be abstracted from medical records for all patients enrolled into the study, as well as all patients prescribed an opioid during the recruitment period of 18-months.

EHR-Based Medication Complete Communication (EMC²) Strategy to Promote Safe Opioid Use: A Physician Randomized Trial

Illinois Prescription Monitoring Program (ILPMP): We will obtain data from the ILPMP on medication fill date, subsequent refills of the prescribed opioid, and new prescriptions for other controlled substances.

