24.0 Confidentiality

24.1 Patients. After identifying eligible subjects, a member of the research staff will approach the patient and obtain written informed consent. Written consent will consist of permission to be contacted for the future phone interviews, permission for possible receiving additional information about their medication, and permission for medical record review. The research assistant will review the consent with participants. He/she will provide participants with information on the study plan and their rights as research participants. Participants' consent will be documented by their signatures. Subjects will be provided with a copy of the consent. They may withdraw at any time during the study without penalty or loss of any healthcare benefit or service to which they are entitled.

Patients who state that they do not want to receive further communication via SMS text-messaging will have the opportunity to cancel the text messages and not receive further outreach; they will be included in outcome assessments.

Data from the Illinois Prescription Monitoring Database will be obtained via individual patient record query for the enrolled patients. No protected health information will not be sent outside of Northwestern or to the State for a database query.

Patients will be assigned a unique identification number; The research database will be password protected and accessible only to the research team. Information linking subjects with their unique identifier will be kept on a separate password-protected desktop computer in a locked office within the Department of Emergency Medicine. We believe that in using these methods we will be compliant with the "Standards for Privacy of Individual Identifiable Health Information" under the Health Insurance Portability and Accountability Act of 1996 (HIPAA) Privacy Rule.

ED physicians, mid-level providers and follow-up providers

All participants will be told that their participation is voluntary; they can stop at any time, and whether they participated or not will not be disclosed to their superiors.

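### Refills and new opioid prescriptions, a secondary measure, rest on participant report by phone, although the prescription monitoring data already being obtained could supply additional opioid fills more completely

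*Protocol*

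**What the plan says.** **Source of the measure.** The secondary endpoint paragraph of Protocol section 8.1 lists "participant report of refills and new opioid prescriptions received" next to the medication diary, patient opinion and risky behaviours. It adds: "Secondary endpoints will be assessed with phone interviews". Section 9.2 gives the final, 1-month call the task to "determine if patients have received additional opioid pain relievers from other providers".

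**What the ILPMP supplies.** Section 9.4 (Sources of Materials) says it will provide "medication fill date, subsequent refills of the prescribed opioid, and new prescriptions for other controlled substances". Section 24.1 says the data "will be obtained via individual patient record query for the enrolled patients", and section 25.3 has two co-investigators access the database directly.

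**How the ILPMP data are used.** The exploratory endpoint in section 8.1 draws its misuse and prescribing indicators from the "Prescription Monitoring Program (ILPMP) at 1-year post initial ED prescription". Section 9.4 lists the ILPMP as a general source without linking it to an endpoint. Neither document makes it the source of the refill and new-prescription measure, or a check on it. The SAP mentions neither the ILPMP nor any refill or new-prescription outcome.

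**Numbers and analysis rules.** Section 4.1 gives "Number of Patients to be Enrolled. N=1500". Section 11.1 anticipates at least 54% retention at the 7-14 day call, and so a minimum of 816 patients (272 per arm). It limits analysis to subjects with roughly 80% or more of the interview completed. Section 13.1 withdraws patients who miss calls and do not respond to three rescheduling attempts.

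**The concern.** Of two sources on closely related events, the plan puts the weaker one in the higher-ranked endpoint and leaves the stronger one to exploratory use.

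Self-report has two weaknesses here. First, patients may not disclose extra opioids, particularly to interviewers who carry a checklist of dangerous opioid behaviours (section 9.3). The intervention arms receive the MedSheet, prompted counselling and, in one arm, text messages on topics that include pill sharing. That could change what patients are willing to say, and so make under-reporting differ by arm. Second, the measure is missing for anyone not reached, and those patients may differ in their use of further opioids. The question about other providers belongs to the last call, for which sections 9.2 and 22.5 list no gift card, although they list one for enrolment and for each earlier call.

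At stake are the credibility and precision of the between-arm comparison of additional opioids. A dispensing record does not depend on disclosure or on answering the phone.

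**Working it through.** **Inputs from the documents.** 1500 enrolled (section 4.1), or 500 per arm if the arms are equal; retention of at least 54% at 7-14 days, with a minimum of 816 patients, 272 per arm and 8 per physician (section 11.1); ICC 0.001 (section 11.2).

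**Assumptions, because the documents give no figure.** Event rate p of 15% or 30%; phone retention of 80% as an alternative to the stated minimum; reporting sensitivities as given below.

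**1. The plan's own count.** 1500 × 0.54 = 810, against 816 stated; 816/1500 = 54.4%, and 3 × 272 = 816. The figure reproduces to within rounding.

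**2. Ratio of standard errors, ILPMP to phone.** At a fixed event rate the ratio is √(n_phone / n_ILPMP).
- Stated minimum: √(272/500) = 0.74.
- Assumed 80% retention, 400 per arm: √(400/500) = 0.89.

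Clustering hardly matters. The design effect is 1 + 7 × 0.001 = 1.007 at 8 patients per physician and 1 + 9 × 0.001 = 1.009 at 10.

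**3. 95% half-width for a difference between two arms,** 1.96 × √(2p(1−p)/n), in percentage points:

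| Assumed p | n = 272 (stated minimum) | n = 400 (assumed 80%) | n = 500 (ILPMP, upper bound) |
|---|---|---|---|
| 15% | 6.0 | 4.9 | 4.4 |
| 30% | 7.7 | 6.4 | 5.7 |

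For example, at 15% and n = 272: 1.96 × √(2 × 0.15 × 0.85 / 272) = 1.96 × 0.0306 = 0.060.

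**4. Differential reporting (illustration only).** If the true rate is the same in both arms, the false difference equals the rate times the gap in reporting sensitivity.
- No gap gives 0.
- Rate 15%, gap of 10 to 15 points: 0.15 × 0.10 = 1.5 points to 0.15 × 0.15 = 2.25 points.
- Rate 20%, reporting of 90% in usual care and 70% under intervention: 18% against 14%, a false 4 points. With 272 per arm and a two-sided 0.025 level, the chance of a significant result in that direction is about 17%, against 1.25% with no bias.

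**5. Can the ILPMP supply a 30-day measure?** The pull is at 1 year, but section 9.4 says fill dates are obtained, so records can be cut to a 30-day window. Section 9.4 also covers "subsequent refills of the prescribed opioid, and new prescriptions for other controlled substances", so the records must be restricted to opioids.

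**The case against.** The case on the other side is substantial, and much of it limits the point.

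- A reader might infer that phone data reach at most 816 patients. Section 11.1 gives 54% and 816 as a conservative minimum, and no 1-month retention is stated. At 80% retention most of the gain in precision disappears. This stands, so the gain is shown as a range.
- A reader might take all 1500 as secured. Section 13.1 withdraws non-responders well before the 1-year pull, and section 13.3 speaks only of keeping data collected up to withdrawal. Section 24.1 says enrolled patients without saying whether the query continues for them. So 500 per arm is an upper bound, and the 80% completion rule would also have to yield. This stands and adds to the fix.
- Refill report may be one input to actual use, alongside the diary, and not an endpoint of its own; the list in section 8.1 is run together and allows either reading. The SAP models safe actual dosing and names no refill outcome. A reader therefore cannot say that a named SAP comparison is biased.
- The two sources do not record identical events. Out-of-state and unfilled prescriptions would be missed by the ILPMP, and a fill is not use.
- A reader might conclude that the whole measure depends on the last call. Only the question about other providers is assigned to it; section 8.1 refers to phone interviews in the plural.
- No passage shows that reporting differs by arm. At an assumed 15% rate, the illustrated 1.5 to 2.25 points lie inside the 4.4-point half-width that remains even with 500 per arm.

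None of this supplies a reason to leave the ILPMP data out of the secondary comparison when they are already being obtained.

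**Conclusion.** The point holds as an inexpensive improvement to a secondary measure. The text is clear that refills and new prescriptions come from participant report by phone, that the ILPMP is queried for enrolled patients, and that neither document connects the two.

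The gain in precision is a standard error of 0.74 to 0.89 times the phone-based value. At an assumed 15% event rate this takes the half-width to 4.4 points, from 6.0 at the stated minimum or from 4.9 at 80% retention. These figures assume equal arms, an ILPMP query that covers every enrolled patient, and an assumed event rate. The protection against concealment and selective non-response is a matter of principle, and its size cannot be determined from the documents.

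The primary endpoint, the sample size and the outcomes named in the SAP are not affected.

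**What to change.** 1. In Protocol section 8.1, define additional opioid fills as any ILPMP-recorded opioid fill other than the index prescription within 30 days of the ED visit, restricted to opioids and cut by fill date, for all enrolled patients by assigned arm.
2. Add this outcome to the SAP with the same mixed model.
3. Exempt it from the 80% interview-completion rule in section 11.1.
4. State in section 13 whether the ILPMP query covers patients withdrawn for non-response, as distinct from those who withdraw consent.
5. Keep participant report as a supportive measure, and leave the diary and risky-behaviour measures unchanged.
6. The SAP is written in the past tense. If the data have already been analysed, label the outcome as added later.

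**Cost.** No new data source is needed. The work is the endpoint wording, one more model, and two clarifications of who is analysed and queried. The downside is that out-of-state and unfilled prescriptions are missed and that fills do not measure actual use. The retained self-report can flag missed prescriptions among patients who are reached.
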